4.2 Gender/Minority/Pediatric Inclusion for Research

We will not exclude potential subjects from participating in this study based on ethnic origin or socioeconomic status. Every attempt will be made to enter all eligible patients in this protocol and therefore address the study objectives in a patient population representative of the entire HNSCC cohort at Thomas Jefferson University Hospital. By the nature of the diseases covered in this trial there is a male predominance with 45,330 cancer cases in men and 16,430 cases in women projected to be diagnosed in 2016 in the US alone (a 2.8:1 ratio). Our plan will be to monitor accrual in our MDG meetings monthly and to assess whether our accrual ratio matches the expected ratio of the disease. If it does not, we will first query the tumor registry at TJUH to assess our recent male to female ratio for head and neck squamous cell cancer, and if there is still a discrepancy, we will create an action plan.

4.3 Strategies for Recruitment and Retention

33 subjects will be recruited. No advertisement will be conducted. Screening requirements include serum measurement of creatinine, aspartate aminotransferase, alanine aminotransferase and alkaline phosphatase taken on a non-fasting blood sample. Potential research subjects will be identified by a member of the patient's treatment team, the protocol investigator, or research team at participating centers from Medical Oncology, Radiation Oncology and Surgical offices. Investigators will screen the patient's medical records for

suitable research study subjects and discuss the study and their potential for enrolling in the research study. Patients will be screened based on pathology, image studies etc. A maximum of 11 patients will be enrolled onto each arm of the trial (see Statistical Analysis Plan).

4.4 Subject Withdrawal

4.4.1 Reasons for Withdrawal

Subjects are free to withdraw from participation in the study at any time upon request.

An investigator may terminate a study subject's participation in the study if:

- Any clinical adverse event (AE), laboratory abnormality, or other medical condition or situation occurs such that continued participation in the study would not be in the best interest of the subject.
- The subject meets an exclusion criterion (either newly developed or not previously recognized) that precludes further study participation.

4.4.2 Handling of Subject Withdrawals or Subject Discontinuation of Study Intervention

Patients who do not have pre- medication initiation and post-biopsy, or are discontinued from the study will not be considered as evaluable for this study and will be replaced.

Patients will be contacted by phone by a study coordinator 30 days (± 5 days) after their planned resection to assess for any further adverse events that were not noted at the time of surgical resection (Visit 2).

4.5 Premature Termination or Suspension of Study

This study may be suspended or prematurely terminated if there is sufficient reasonable cause. Written notification, documenting the reason for study suspension or termination, will be provided by the suspending or terminating party to investigator, and regulatory authorities. If the study is prematurely terminated or suspended, the principal investigator will promptly inform the IRB and will provide the reason(s) for the termination or suspension.

Circumstances that may warrant termination include, but are not limited to:

- Determination of unexpected, significant, or unacceptable risk to subjects.
- Insufficient adherence to protocol requirements.
- Data that is not sufficiently complete and/or evaluable.
- Determination of futility.

5 Study Intervention

5.1 Study Product

The investigator shall take responsibility for and shall take all steps to maintain appropriate records and ensure appropriate supply, storage, handling, distribution and usage of investigational product in accordance with the protocol and any applicable laws and regulations.

5.2 Study Product Description

Metformin:

Metformin is a biguanide drug currently approved for the treatment of type 2 diabetes mellitus by the FDA. It is currently being investigated in multiple cancer treatment trials.

Metformin is a therapeutic agent in the protocol. The initial starting dose will be 500mg orally daily for 3 days which then will be increased to 500 mg twice daily and, if tolerated, further increased to 1000mg twice daily after day 6. Patients will maintain 1000 mg twice a day dosing until the day prior to their scheduled definitive surgery. This dose schedule has been shown to be well tolerated and was able to promote cellular changes consistent with beneficial anti-cancer effects in breast cancer patients.

The treatments to be used in this trial are outlined in Table 1.

Doxycycline:

Doxycycline is an antibiotic provided in the formulation doxycycline hyclate. Doxycycline is virtually completely absorbed after oral administration. Following administration of a single 200 mg dose to adult volunteers, average peak serum doxycycline levels were 2.6 mcg/mL at 2 hours, decreasing to 1.45 mcg/mL at 24 hours. The mean Cmax and AUC 0-∞ of doxycycline are 24% and 13% lower, respectively, following single dose administration of DORYX tablets, 100 mg with a high fat meal (including milk) compared to fasted conditions. The mean Cmax of doxycycline is 19% lower and the AUC 0-∞ is unchanged following single dose administration of DORYX Tablets, 150 mg with a high fat meal (including milk) compared to fasted conditions. The clinical significance of these decreases is unknown.

Tetracyclines are concentrated in bile by the liver and excreted in the urine and feces at high concentrations and in a biologically active form. Excretion of doxycycline by the kidney is about 40%/72 hours in individuals with a creatinine clearance of about 75 mL/min. This percentage may fall as low as 1-5%/72 hours in individuals with a creatinine clearance below 10 mL/min.

Studies have shown no significant difference in the serum half-life of doxycycline (range 18-22 hours) in individuals with normal and severely impaired renal function. Hemodialysis does not alter the serum half-life.

Doxycycline is an FDA approved product that is indicated for the prophylaxis against and treatment of both bacterial and protozoal infections. For adults the dose is 200 mg on the first day of treatment administered as 100 mg every 12 hours followed by a maintenance dose of 100 mg daily. The maintenance dose may be administered as a single 100 mg dose of 50 mg dose every 12 hours. Serious infections are treated with a sustained dose of 200 mg per day in

divided doses. Treatment for uncomplicated bacterial infections typically lasts for 7 days total. Prophylaxis for malaria can be continued daily for the period of time the patient is in a malarious area and continued for 4 weeks thereafter, up to 4 months. Our planned dosing is to use 100 mg every twelve hours until the day prior to their scheduled definitive surgery.

Table 1 Trial Treatments

DRUG	DOSE LEVEL	DOSE	ROUTE	REGIMEN
METFORMIN	1	500 mg daily	Oral	Day 1-3
	2	500 mg every 12 hours (1000mg daily)	Oral	Day4-6
	3	1000 mg every 12 hours (2000 mg daily)	Oral	Day 7-the day prior to surgery
DOXYCYCLINE	-1	100 mg daily	Oral	Only if needed for inability to tolerate level 1
	1	100 mg every 12 hours (200 mg daily)	Oral	Day 1-the day prior to surgery

The same dosing and modifications apply either when given alone or together.

5.2.1 Acquisition

Drug will be obtained through the hospital drug pharmacy and maintained by the Investigational Drug Service Pharmacy.

5.2.2 Formulation, Packaging, and Labeling

Metformin:

Metformin will be provided as 500 mg tablets which are round, white to off-white, film-coated tablets. These are stored at 20°–25° C (68°–77° F); excursions permitted to 15°–30° C (59°–86° F). [See USP Controlled Room Temperature.] It will be dispensed in light-resistant containers labelled as metformin.

Doxycycline:

Doxycycline will be provided as 100 mg white oval tablets containing yellow pellets. These are stored at 25°C (77°F); excursions permitted to 15°-30°C (59°-86°F) [see USP Controlled Room Temperature]; dispense in a tight, light-resistant container (USP) labelled as doxycycline.

5.2.3 Product Storage and Stability

Drug will be stored in a locked cabinet until given to the participants at room temperature in the Thomas Jefferson University Hospital Investigational Drug Service (IDS) Pharmacy. Access to the locked cabinet will only be granted to the pharmacist. The investigator must ensure that it is stored in accordance with the environmental conditions as defined in the Investigator Brochure. Clinical supplies may not be used for any purpose other than that stated in the protocol.

Each drug is stable at room temperature as above.

5.3 Dosage, Preparation, and Administration

Clinical supplies will be affixed with a clinical label in accordance with regulatory requirements.

5.4 Dose Modifications and Dosing Delays

Particular attention will be paid in the first three days of treatment. Patients will take 500mg/day for 3 days. From day 4, 500mg twice daily and then in 3 days (day 7) dose escalation to 1000mg twice daily will be achieved. This will be taken until the day before surgery after dinner. A phone call on the day before (or \pm 2 days) each dose escalation will be made in order to evaluate the tolerability of the drug and also weekly thereafter. Patients will be instructed to contact the clinical investigators should any toxicity occur during the study (66).

Metformin will not be started if CT scan with intravenous contrast is administered to decrease risk of lactic acidosis. After the scan they will be instructed to start the metformin the following day. This approach is more stringent than the most recent recommendation of the American College of Radiology which does not recommend holding metformin in the absence of comorbidities (renal insufficiency, liver dysfunction, alcohol abuse, cardiac failure, myocardial or peripheral muscle ischemia, sepsis or severe infection) which are exclusion criteria for this clinical trial (29).

Toxicity will be evaluated using the most recent version (version 4) of the NCI toxicity criteria, i.e. the NCI Common Terminology Criteria for Adverse Events (CTCAE) version 4.0.

- Grade 1 toxicity: Patient will be maintained on full dose.
- Grade 2 toxicity: Dose will be reduced by 50% until grade 1 or lower. If symptoms are not resolved within 3 days the treatment will be discontinued definitively.
- Grade 3 toxicity (probably or definitely drug related): Treatment will be interrupted and toxicity reassessed daily. If toxicity improves to grade 2, dose will be reduced by 50%.
- Grade 4 toxicity (probably or definitely drug related): Treatment will be discontinued definitively.

In case of grade 1 or 2 diarrhea (the most frequent side effect) a concomitant administration of loperamide will be provided.

Clinical supplies will be affixed with a clinical label in accordance with regulatory requirements.

If doses of either medication are missed due to toxicity they should not be replaced. If a dose is not taken due to an error, it may be taken up to 6 hours later. If vomiting occurs within 30

minutes of intake, that dose may be repeated. These events should be recorded by the patient on their pill diary.

5.5 Study Product Accountability

Metformin and doxycycline tablets will be provided by the Department of Medical Oncology and will be coordinated through the Thomas Jefferson University Hospital Investigational Drug Service (IDS) Pharmacy. Drug will be stored in locked cabinet in the IDS pharmacy until given to the participants. An approximately 2-week supply of metformin and/or doxycycline will be provided to subjects and the drug will be self-administered by the participants.

Upon receipt of the of the study treatment supplies, an inventory must be performed and a drug receipt log filled out and signed by the person accepting the shipment. It is important that the designated study staff counts and verifies that the shipment contains all the items noted in the shipment inventory. Any damaged or unusable study drug in a given shipment (active drug or comparator) will be documented in the study files. The investigator must notify study sponsor of any damaged or unusable study treatments that were supplied to the investigator's site. At the completion of the study, there will be a final reconciliation of drug shipped, drug consumed, and drug remaining. This reconciliation will be logged on the drug reconciliation form, signed and dated. Any discrepancies noted will be investigated, resolved, and documented prior to return or destruction of unused study drug. Drug destroyed on site will be documented in the study files.

The investigator is responsible for keeping accurate records of the clinical supplies received from the Sponsor or designee, the amount dispensed to the subjects and the amount remaining at the conclusion of the trial.

Upon completion or termination of the study, all unused and/or partially used investigational product will be destroyed at the site per institutional policy. It is the Investigator's responsibility to arrange for disposal of all empty containers, provided that procedures for proper disposal have been established according to applicable federal, state, local and institutional guidelines and procedures, and provided that appropriate records of disposal are kept.

5.6 Assessing Subject Compliance with Study Product Administration

Upon enrollment to the trial, depending on which arm the patient is enrolled to, there will be either one or two pill bottles with the appropriate number of metformin and doxycycline tablets distributed to the patients. The pill bottles will be accompanied with detailed instructions on the proper dosage/number of tablets to take daily as noted above. Upon arrival for definitive surgical resection, the bottle will be collected by our trial coordinator and the contents will be evaluated for compliance.

5.7 Concomitant Medications/Treatments

Medications or vaccinations specifically prohibited in the exclusion criteria are not allowed during the ongoing trial. If the patient is on any of the Class C medications as outlined in Section 5.4.2, they should be monitored closely for any potential interactions or side effects. If there is a clinical indication for one of these or other medications or vaccinations specifically prohibited during the trial, discontinuation from trial therapy or vaccination may be required. The investigator should discuss any questions regarding this with the Sponsor. The final decision on

any supportive therapy or vaccination rests with the investigator and/or the subject's primary physician. However, the decision to continue the subject on trial therapy or vaccination schedule requires the mutual agreement of the Investigator, the Sponsor, and the subject

All treatments that the investigator considers necessary for a subject's welfare may be administered at the discretion of the investigator in keeping with the community standards of medical care. All concomitant medication and therapies will be recorded on the case report form (CRF) including all prescription, over-the-counter (OTC), herbal supplements, and IV medications and fluids. If changes occur during the trial period, documentation of drug dosage, frequency, route, and date should also be included on the CRF. These will be cross referenced against the list of drugs in section 4.2 (Exclusion Criteria) to ensure that no agents that are contraindicated with metformin or doxycycline are used.

All concomitant medications received within 28 days before informed consent is signed and 30 days after the last dose of trial treatment should be recorded. Concomitant medications administered to treat SAEs and ECIs should be recorded as defined

All medications are permitted except those that are contraindicated with metformin and doxycycline under current FDA recommendations. It is important to note that the medications that are contraindicated with metformin are contraindicated due to concern for theoretical interactions. Class C medications are allowed if they are established at baseline. The treating physician should be made aware of any new Class C medications taken during therapy for proper monitoring of potential interactions. The following is a list of medications identified as class C (monitor therapy) and class D (consider therapy modification) when treatment with metformin or doxycycline is considered:

Class C:

Carbonic anhydrase inhibitors
Cephalexin
Corticosteroids (orally inhaled)
Corticosteroids (systemic)
Dalfampridine
Dofetilide
Glycopyrrolate
Lamotrigine
Luteinizing hormone-releasing hormone analogs
Pegvisomant
Penicillin
Trospium

Class D:

Bismuth Subsalicylate
Cimetidine
Iodinated contrast agents
Somatropin

5.8 Dietary Restrictions

Subjects should maintain a normal diet unless modifications are required to manage an AE such as diarrhea, nausea or vomiting. Patients will be asked to fill a dietary log at the beginning the study when they speak with a registered dietician.

6 Study Schedule

All patients will be evaluated by a treating surgeon. Initial visit will include overall assessment of health as well as determination of eligibility. A study calendar details the requisite pretreatment evaluations

Study Procedure	Screening	Treatment/Intervention Period ^D						End of ^E Treatment	Follow-up ^G
		Week 1			Week 2 ^D	Week 3-5			
		Day 1 -7			Day 8-14		Surgical ^F Resection	Week 6	Week 7
Administrative Procedures									
Informed consent ^A and research authorization/ HIPAA form	X								
Inclusion/Exclusion Criteria	X								
Demographics, Medical history	X								
Clinical Assessment									
Physical examination, vitals, weight, blood pressure	X							X ^N	x
Height	X								
ECOG Performance status	X								X
Pathology Report histologic confirmation of disease if available ^I	X							X	-
Concomitant meds ^K	X	X	X	X	X	X	X	X	X
Toxicity and AE Assessment ^K	X	X	X	X	X	X	X	x	x

Laboratory tests ^B										
Hematology	X									
Blood Chemistry	X									
pregnancy test ^H	X									
Treatment/ Intervention										
Metformin ^{C,D}		X	X	X	X	X	X			
Doxycycline ^{C,D}		X	X	X	X	X	X			
Diagnostic Biopsy or tumor sample ^I	X							X		
Surgical Resection								X		
Correlative Studies										
Serologic metabolic profile (miR21 and exosomes) ^F		X						X		
Nutrition Assessment*		X ^M								

*Nutrition assessment and Harris Benedict Equation will occur on Day 1 (or up to Day 8) of enrollment when possible, and may be done via a phone interview.

A. Written informed consent must be obtained before any study-specific screening assessments are performed. Lab results performed as standard-of-care prior to obtaining informed consent and within 28 days prior to enrollment may be used; such tests do not need to be repeated for screening. Trial treatment should begin within 5 days of eligibility confirmation.

B. Blood Chemistry includes: Creatinine, AST, ALT, ALK Phos, T Bili $> 2.5 \times$ ULN. Hematology includes: CBC (with differential). All are non-fasting labs.

C. Study treatment follow up phone calls will occur on days 3 and 5 ± 2 days of dose escalation to evaluate tolerability, document AEs, and concomitant medications. If patient remains on study drugs for >7 days, study treatment follow-up phone calls will occur a minimum of once a week until surgery to evaluate tolerability, AEs, and con meds. Last doses of metformin and/or doxycycline pills should not be taken within 12 hours of scheduled surgery.

D. Patient must receive a minimum of 7 days of metformin and/or doxycycline before having definitive surgery. Patients will stay on metformin and/or doxycycline until the day prior to surgery (up to the maximum of 5 weeks).

E. End of treatment visit may occur within 14 days ± 7 days of stopping study drug.

F. Correlative study blood to be collected the morning of surgical resection. Baseline samples are to be drawn after enrollment but prior to start of study treatment.

- G. Follow up phone call will be performed 30 days after last dose of study medication for any other side effects or toxicity and for pathologic staging information.
- H. serum or urine pregnancy test must be done within 14 days prior to enrollment on study for all women of childbearing potential
- I. If a confirmatory biopsy is performed at TJUH and excess tissue is available tissue will be flash frozen both at the time of biopsy and at the time of resection. A post-treatment tissue sample will be obtained from excess tissue taken from this resection specimen that is not needed in the course of clinical care.
- J. Study drug stopped the night prior to surgery.
- K. Concomitant medication reconciliation, and Toxicity and Adverse Event assessments should be done at every patient contact to fully capture any potential dose limiting toxicities or AEs that affect the patient's ability, willingness, and eligibility to continue taking study medications.
- L. Operative reports should be included with pathology reports in source documents when applicable.
- M. To be performed by a registered dietician, when possible. Must meet with patient within five days of enrollment and record the patient's last 3 days of caloric intake and estimate their caloric intake versus their caloric needs per the Harris Benedict Equation. It will be noted in the patient chart if these assessments could not be completed.
- N. Pre-operative nursing or anesthesia exam is acceptable and is to be performed the morning of surgery.

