2.2.2 Secondary

- Assess safety and tolerability of metformin and doxycycline treatment in subjects with cancer. Toxicity will be evaluated using the most recent version (version 4) of the NCI toxicity criteria, i.e. the NCI Common Terminology Criteria for Adverse Events (CTCAE) version 4.0. A copy of the CTCAE can be found at <http://ctep.cancer.gov>. Any grade 3 or 4 SAE will require immediate notification to the DSMB and IRB.
- Assess the change in the percent of tumor cells expressing MCT4, that are TUNEL positive and that express MCT1, BGAL and TOMM20 in HNSCC tumors using semiquantitative scoring and digital pathology using Aperio analyses of expression intensity with previously validated algorithms.

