3.6 Study Timeline

3.6.1 Primary Completion

Eligibility Screening: Trial Coordinator will screen the office charts for possible inclusion in the trial. Labs for the screening part will be available from pre-admission testing that is standard of care for initial biopsy.

Visit 1, Day 0: Subjects that meet the inclusion criteria after reviewing plan for tissue diagnosis, laboratory data and clinical chart will be approached the day of their follow up with a subspecialty surgeon. The initial biopsy does not need to take place on Day 0 and previously obtained tissue may be used. The study coordinator will meet with the prospective candidates and go over the protocol, answer questions and obtain informed consent. Once the subject's laboratory results are reviewed and eligibility is confirmed, the patient will be randomized and metformin and/or doxycycline will be dispensed. Medication will be dispensed from Thomas Jefferson University Investigational Drug Service (IDS) Pharmacy after randomization. Instructions on how to take study drug will be given and times for follow up phone calls for tolerability and safety will be arranged with participants. Patients will also be asked to meet with a nutritionist either in person or by phone within the first 8 days of their enrollment to fill out a 3-day dietary recall log when possible. A nutritionist will either meet with the patients in person or call them within the first 8 days of their enrollment to fill out the 3-day dietary recall log. The nutritionist will do a 2-day guided recall, recording what the patients have eaten in the last 3 days and how much. Two 15 mL vials of blood will be drawn for baseline metabolomics and exosome profiling.

Visit 2, Day of Surgery, Week 1-5 based upon surgery: On the day of surgery, two 15 ml vials of blood will be drawn for post-treatment metabolomic and exosome profiling. A post-treatment tissue sample will be obtained from excess tissue taken from this resection specimen that is not needed in the course of clinical care. On either the day of surgery or up until their first post-op visit, patients will be approached for bottles and pill reconciliation as well as follow up of side effects and adverse events. For patients who, per institutional standard of care, have genetic testing performed on their tumor sample, we will review this information in addition to the remainder of their pathology report.

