7.1 Study Procedures/Evaluations

- Medical history including intercurrent illnesses and specific attention to diabetes, may be obtained from the medical record
- Physical exam: height, weight, obtained from the medical record

- Concomitant meds: prescription medications taken for the 28 days prior to enrollment
- ECOG performance status from the medical record
- Obtain histologic confirmation of disease from the medical record
- Laboratory tests: Hematology- CBC with differential; Blood Chemistry- Creatinine, AST, AT, ALK Phos T Bili to have been performed within 28 days of enrollment and thus may be obtained either from the medical record or as a part of the standard of care

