8.1.2 Adverse Events

An adverse event is any untoward or unfavorable medical occurrence in a human subject, including any abnormal sign (for example, abnormal physical exam or laboratory finding), symptom, or disease, temporally associated with the subject's participation in the research, whether or not considered related to the subject's participation in the research.

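### Safety laboratory tests are scheduled only at screening, so laboratory toxicity can reach the safety tables and the stopping count only through incidental results

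*Combined protocol and SAP*

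**What the plan says.** **What depends on laboratory information.** Section 2.2.2 sets a secondary endpoint: "Assess safety and tolerability of metformin and doxycycline treatment in subjects with cancer", graded by CTCAE version 4.0. Section 8.1.2 defines an adverse event as "including any abnormal sign (for example, abnormal physical exam or laboratory finding". Section 8.5 monitors acute toxicity by CTCAE during therapy and for 30 days after resection. Section 11.1 hypothesises that the drugs, alone or together, are safe and tolerable before surgery. Section 11.2 reports safety in descriptive tables, and the table in 11.2.1 counts patients with Grade 3 or higher toxicity. Among the grounds on which an investigator may end participation, Section 4.4.1 lists: "Any clinical adverse event (AE), laboratory abnormality, or other medical condition or situation occurs". It also lists a newly developed exclusion criterion.

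**When the tests are done.** In the Section 6 calendar, hematology and blood chemistry each carry one mark, under screening. Note B names creatinine, AST, ALT, alkaline phosphatase and total bilirubin, and adds: "Hematology includes: CBC (with differential). All are non-fasting labs". Three further places agree on timing:
- Section 4.3: "Screening requirements include serum measurement of creatinine, aspartate aminotransferase, alanine aminotransferase and alkaline phosphatase taken on a non-fasting blood sample".
- Section 7.1 describes the tests as "to have been performed within 28 days of enrollment and thus may be obtained either from the medical record".
- Section 6.1 lists them within the screening window.

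Section 7.2.1 names the tests without a time point. Note A of the calendar widens the window backwards: "Lab results performed as standard-of-care prior to obtaining informed consent and within 28 days prior to enrollment may be used".

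**Blood after treatment.** Section 3.6.1 has one later draw: "On the day of surgery, two 15 ml vials of blood will be drawn for post-treatment metabolomic and exosome profiling". Section 6.3 lists research correlatives for that visit and no clinical chemistry or CBC.

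**The concern.** The protocol grades toxicity on a scale that includes laboratory abnormalities, but it schedules no test that would reveal one after dosing starts. Symptomatic events will be found by the calls and visits. A rise in creatinine or transaminases, or a fall in blood counts, that causes no symptoms will be found only if someone orders a test for another reason and the result is carried into the study record.

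The error runs one way. An event that is not looked for can lower the observed count but cannot raise it, so the safety tables and the stopping count lean toward safety in all three arms. The affected organs are ones that Section 1.4.1 itself raises: it links lactic acidosis risk to renal and hepatic compromise, and it lists rare hepatotoxicity with tetracyclines. The combination arm is the most exposed, because Section 1.4.1 expects no excess toxicity from the pair and the prior in 11.2.1 is built from single-agent experience.

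**Working it through.** **1. Contacts and what each one schedules**

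| Contact | Where | Scheduled safety content | CBC, creatinine or liver tests |
|---|---|---|---|
| Screening | 4.3, 6.1, 7.1, calendar | Exam, history, laboratory panel | Yes |
| Baseline | 6.2 | Exam, concomitant medications, research tubes | No |
| Calls around escalation, then at least weekly | 5.4, calendar note C | Tolerability, adverse events, concomitant medications | No |
| Visit 2, day of surgery | 3.6.1, 6.3 | Exam, adverse events, concomitant medications, research blood | No |
| End of treatment | 6.4 | Adverse events, concomitant medications | No |
| 30-day call | 6.5 | Adverse events | No |

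Scheduled safety laboratory measurements after screening: 0 per patient in each arm. This does not rest on the layout of one extracted table, because Sections 4.3, 6.1 and 7.1 place the tests before enrolment and Sections 6.3 to 6.5 omit them.

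**2. Age of the only required value**

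Inputs: results accepted up to 28 days before enrolment (note A); treatment to begin within 5 days of eligibility confirmation (note A); at most 35 days of dosing (Section 1.2, dosage rationale; note D).

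- Dosing starts at enrolment: 28 days old at first dose, and 28 + 35 = 63 days at resection.
- The start window is also used, with eligibility confirmed at enrolment: 28 + 5 = 33 days at first dose, and 33 + 35 = 68 days at resection.

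**3. The stopping boundaries, and what they assume about ascertainment**

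Section 11.2.1 gives the prior Beta(0.04, 1.96) and stops when the posterior probability of a rate of 5% or more exceeds 90%. With r events in n patients the posterior is Beta(0.04 + r, 1.96 + n − r).

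| Events / patients | P(rate ≥ 5%) | Stop? |
|---|---|---|
| 2 / 10 | 0.905 | Yes |
| 2 / 11 | 0.889 | No |
| 3 / 22 | 0.900 (just above the cut-off) | Yes |
| 3 / 23 | 0.890 | No |
| 4 / 35 | 0.901 | Yes |
| 4 / 36 | 0.893 | No |

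The printed boundaries (2 at 10, 3 at 11–22, 4 at 23–35, 5 at 36) reproduce exactly, so no figure in the plan is wrong. The calculation treats r as fully observed. At 10 patients the boundary is 2, so one unseen Grade 3 laboratory event out of two true events would leave r = 1 and the study would continue.

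**4. Size of the loss**

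Let p be the true rate of asymptomatic Grade 3 or higher laboratory toxicity and c the fraction that routine care happens to capture. The expected number missed in n patients is n × p × (1 − c). The documents give neither p nor c. Across c from 0 to 1 the loss runs from all such events to none, so only its direction is fixed.

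**The case against.** The strongest case against runs as follows.

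- **Routine results are not barred.** Section 15.3 lists laboratory studies among the data collected, calendar note K asks for adverse event assessment at every contact, and Section 8.1.2 admits laboratory findings. A pre-operative result in the chart could be recorded and counted. This stands. A reader might infer that laboratory toxicity cannot enter the tables or the stopping count at all; the documents do not support that. But nothing requires such results to exist, to be dated after the first dose, or to be abstracted for every patient.
- **Section 4.4.1 is discretionary.** It says that an investigator may end participation, and that power can act on any result that comes to light. Exclusion criterion 11 needs a hepatic history together with abnormal tests, so a new liver-test rise alone would not meet it. This stands. The documents do not support reading 4.4.1 as a mandatory laboratory rule that the schedule disables.
- **The listed risks are small.** Section 1.4.1 gives lactic acidosis as 3 per 100,000 patient-years and says that this may be overstated. With 22 metformin patients for at most 35 days, exposure is 22 × 35 / 365.25 ≈ 2.1 patient-years, and 2.1 × 3 / 100,000 ≈ 0.00006 expected cases. This argues against alarm. It says nothing about the rate of asymptomatic creatinine, liver or blood-count changes, which the plan does not give.
- **The longest intervals are extremes.** Section 3.6.1 takes screening results from pre-admission testing for the initial biopsy, and Section 1.2 gives an average of 3 weeks from biopsy to surgery. A typical value would then be about 3 weeks old at resection. This stands: 63 and 68 days are what the rules permit, not what is usual.

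Screening-only testing for two approved drugs over 1–5 weeks can be defended as a lean design. It does not by itself support a safety conclusion that covers laboratory toxicity.

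**Conclusion.** The point holds in this form: no safety laboratory test is scheduled after screening in any arm, so laboratory toxicity is captured unsystematically and the secondary safety conclusion is biased toward safety. The same gap affects the Grade 3 or higher count in Section 11.2.1, whose boundaries are computed correctly but presume that such events are seen.

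The size is 0 scheduled post-screening measurements. The required value is permitted to be up to 63 days old at resection, or 68 if the start window is used and eligibility is confirmed at enrolment. The number of events lost cannot be estimated from the documents.

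A reader might also infer that a test at Visit 2 would restore laboratory-based withdrawal. It would not, because Sections 3 and 6.3 end dosing at least 12 hours before surgery.

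The primary CAV1 analysis is unaffected. The gap should be closed because it touches a stated endpoint and a stopping count and is inexpensive to repair.

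**What to change.** 1. In the calendar and Section 6.3, require creatinine, AST, ALT, alkaline phosphatase, total bilirubin and CBC to be recorded for every patient at Visit 2. Use pre-operative results obtained after the start of study drug where they exist, with their dates. Otherwise run a routine panel with the draw already planned that morning.
2. Confirm first that the research tubes suit this purpose. Section 7.2.2 describes serum separator tubes sent directly to a research laboratory, and serum cannot give a CBC. One added clinical tube at the same draw may be needed.
3. In the descriptive safety tables, report the shift from screening by CTCAE grade and arm, with the number of patients who have both values.
4. Count Grade 3 or higher laboratory events under 11.2.1.
5. State in 11.2 that laboratory toxicity is assessed only at this time point, and word the safety conclusion accordingly.
6. Separately, the sponsor should reconcile the laboratory-based withdrawal reasons in 4.4.1 with the schedule. Whether to test during treatment is its clinical decision, and nothing here proposes a dosing or withdrawal rule.

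**Cost.** One chart abstraction or routine panel per patient, possibly one extra tube, and perhaps slightly less research serum. No extra visit and no separate venipuncture are needed.
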